## General Study Design

We will employ a three-arm, active-controlled, randomized crossover trial to assess the safety and efficacy of CICADAS app in adolescents with ASD, and to evaluate its potential as a stand-alone treatment, as a primer for PEERS, or as a treatment enhancer of PEERS. We will randomize adolescents with ASD (ages 11-18) to CICADAS only, PEERS + CICADAS app, or PEERS + Active Control app.

Approximately 56 participants will be consented to ensure the successful completion of 48 participants (16 participants per treatment arm). A diagnostic interview will be performed to determine eligibility. Following inclusion and enrollment, participants will complete a set of assessments prior to the intervention to establish their baseline performance. Participants will then be randomized to the CICADAS only group (Arm A), PEERS + CICADAS app group (Arm B), or PEERS + Active Control app group (Arm C) and spend up to 16 weeks engaged in their assigned intervention. After 16 weeks, a full battery of assessments will be administered. For the next 16 weeks, Arm A will continue with PEERS only and Arms B and C will receive no treatment during this period. At the end of the intervention period, a full battery of assessments will be administered a second time to evaluate changes in performance. Finally, participants will be asked to fill out an online exit survey to rate enjoyment, usability, perceived benefits, and ease of fit into schedule.

During the first intervention period, participants assigned to the CICADAS only will complete NB-SCT exercises for 16 weeks. Participants assigned to PEERS + CICADAS will engage with the CICADAS app and complete weekly 1-hour PEERS group sessions for 16 weeks. Participants assigned to receive the PEERS + Active Control will engage in the Active Control app and complete weekly 1-hour PEERS group sessions for 16 weeks. During the second intervention period, participants assigned to receive PEERS only will complete weekly 1-hour PEERS group sessions for 16 weeks. During both intervention periods, these participants may have weekly electronic check-ins with site study personnel (as needed). The CICADAS app and the Active Control app icons, design and user experience will look the same as to not unblind the participants.

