Each PEERS group session will consist of a minimum cohort of 3 participants and will meet as a group during the 16 week period. The PEERS clinician will meet with each participant individually for a brief introduction and orientation. The PEERS group sessions will be made available to meet in person or remotely. For remote PEERS group sessions, the study

coordinator and/or PEERS Clinician will create a virtual room open only to cohort participants, explain their role, and make introductions. Next, the PEERS clinician will invite participants to attend weekly 1-hour PEERS group sessions.

The protocol will be conducted in accordance with the protocol submitted to and approved by the reviewing Institutional Review Board and approval will be obtained prior to implementation.

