### Treatment Arms

**Arm A:** Participants assigned to Arm A will engage in CICADAS only for the first 16 weeks of the intervention period. After the completion of the first intervention period and the mid-intervention assessment (V3) visit, these participants will then be assigned to the PEERS only group for the second 16 weeks of the intervention period.

**Arm B:** Participants assigned to Arm B will engage in PEERS + CICADAS for the first 16 weeks of the intervention period. After the completion of the first intervention period and the mid-intervention assessment (V3) visit, these participants will then be assigned to No-Contact (no active intervention) for the second 16 weeks of the intervention period.

**Arm C:** Participants assigned to Arm C will engage in PEERS + Active Control for the first 16 weeks of the intervention period. After the completion of the first intervention period and the mid-intervention assessment (V3) visit, these participants will then be assigned to No-Contact (no active intervention) for the second 16 weeks of the intervention period.

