- Second, individual sessions will be held between the site study coordinator and/or PEERS clinician and each participant to educate them regarding confidentiality prior to entering the intervention. Participants will be informed that 1) they have the right to choose an alias rather than their first name and decide at any point what information they choose to disclose; 2) the PEERS clinician will respect the patients' ability to choose what they disclose, and keep the promises of faithfulness and loyalty to all participants, including not revealing information participants disclose; 3) the PEERS clinician cannot promise that other group members will maintain confidentiality; 4) the PEERS clinician may have a legal obligation to break confidentiality in certain circumstances (e.g., child abuse), and those circumstances will be fully explained. The PEERS clinician will follow established procedures appropriate for their local jurisdiction to report such knowledge; 5) the research teams will be monitoring the Zoom contents, including chat history, throughout the intervention and as such any volunteered information that may be personally identifying will be available to research study monitors.
- Third, participants will be asked to read, sign and agree to be bound by a modified version of the American Psychological Association procedures and guidelines for group therapy (<http://www.apadivisions.org/division-49/publications/newsletter/group-psychologist/2011/04/group-procedures.aspx>), adapted for the target population, while in the intervention.
- Finally, during the first group session, the PEERS clinician will encourage group members to embrace the concept of confidentiality, making it their own rather than a mandatory rule.

Given that one of the goals of CICADAS is to enhance social functioning in individuals with ASD, we will not discourage group members from sharing contact information and befriending other study participants. Research shows that peer-to-peer interactions occur

naturally on social media platforms and serve many purposes, such as establishing new relationships, maintaining relationships, reconnecting with people, disclosing personal experiences of living with ASD, seeking and sharing information related to symptoms and medications.

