## Blinding

Un-blinded Roles: PEERS clinicians and the site study coordinator are un-blinded in order to lead group sessions and support for participants using their assigned programs. They will be distinct from staff administering and scoring assessments. Additionally, designated personnel that are un-blinded may not participate in the assessment and evaluation at Mid-Intervention (V3) or Post-Intervention (V4) assessment visits of study participants.

Blinded Roles: All site staff responsible for the administration and scoring of participant assessments visits conducted after randomization will remain blinded to participant treatment. The Site Principal Investigator will be required to complete a Delegation of Authority Form, indicating which activities individual research team members will be authorized to complete. Principal Investigators will also remain blinded.

Depending upon the extent to which they are responsible for data collection and/or entry, *site study coordinators* may or may not remain un-blinded to participant treatment. This will be clarified on a site-by-site basis and will be noted on the Site Principal Investigator Delegation of Authority Form.

To prevent un-blinding, the following will occur:

1. The treatment arms will be identified as “Arm A, Arm B, and Arm C.”

2. Participants will be reminded not to discuss details related to treatment with blinded psychometricians and/or clinical evaluators during the informed consent process as well as prior to initiation, and at the conclusion of, each assessment visit;
3. Site study personnel will be instructed to not discuss details of either treatment arm during open participant groups or forums outside of the assigned group sessions or cohort discussions;
4. Site study personnel will be required execute the protocol in a manner that minimizes the possibility of accidental un-blinding of psychometricians or clinical evaluators (e.g. unintended viewing of treatment sessions);

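### No blinding safeguard covers talk between participants, so Arm B and Arm C participants can compare apps and unblind the exploratory B–C comparison

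*Protocol*

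**What the plan says.** **Intent.** Protocol, General Study Design: "The CICADAS app and the Active Control app icons, design and user experience will look the same as to not unblind the participants". The Active Control app paragraph under Treatment Interventions adds that the games are meant to be credible as training and to match expectation between the two apps. Arms B and C are therefore meant to be blind to app.

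**Safeguards.** The Blinding section lists four:
- Item 1 labels the arms A, B and C.
- Item 2 is the only rule on what participants may say: "Participants will be reminded not to discuss details related to treatment with blinded psychometricians and/or clinical evaluators".
- Item 3 is addressed to site study personnel, who are to "not discuss details of either treatment arm during open participant groups or forums outside of the assigned group sessions or cohort discussions".
- Item 4 asks staff to avoid accidentally unblinding psychometricians and evaluators.

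**Setting.** Under Treatment Arms, "Participants assigned to Arm B will engage in PEERS + CICADAS for the first 16 weeks of the intervention period", and Arm C receives PEERS with the control app over the same period. On cohorts, General Study Design gives only a minimum size: "Each PEERS group session will consist of a minimum cohort of 3 participants and will meet as a group during the 16 week period". Group leaders know the assignments: "PEERS clinicians and the site study coordinator are un-blinded in order to lead group sessions". On contact between members, Confidentiality says "we will not discourage group members from sharing contact information and befriending other study participants".

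**The concern.** The two apps may share icons and layout, but their content differs in ways that a participant can describe in a sentence. CICADAS uses emotional faces, prosody and gaze matching; the control uses games such as Lineup Four and Bricks Squasher II. Matched appearance protects the blind only while participants do not compare notes, and nothing in the Blinding section asks them not to.

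B versus C is the only comparison that holds PEERS constant and changes only the app. It bears directly on the enhancer question in the SAP's exploratory hypothesis (a). Several of its outcomes come from the family: the SAP labels the SRS-2 and SSIS-RS parent report, and the Protocol labels the CBCL parent report and the YSR self-report. The PedsQL is also collected, although the documents name no informant for it. A blinded assessor does not protect a rating made by a parent or adolescent who knows the app. The SAP says that these data will be used to power a Phase II trial, so a B–C difference partly due to expectation could carry into that sample size.

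**Working it through.** **1. Does any rule cover participant-to-participant talk?**

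| Blinding item | Who is bound | What is covered | Talk between participants? |
|---|---|---|---|
| 1 | Study team | Arm labels | No |
| 2 | Participants | Talk with blinded assessors | No |
| 3 | Site staff | Open groups or forums, outside assigned sessions and cohort discussions | No |
| 4 | Site staff | Accidental unblinding of assessors | No |

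The gap is the absence of a participant-to-participant rule. The exemption in item 3 is a second, smaller gap: it leaves unblinded staff free to discuss app details inside assigned sessions.

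**2. Can Arms B and C meet?** Both attend PEERS in the first period. General Study Design and the PEERS paragraph under Treatment Interventions fix a minimum cohort of 3 and say nothing on arm. Item 3 itself contemplates open participant groups and forums, and Confidentiality leaves outside contact open. Meeting is therefore possible within PEERS if cohorts are mixed, and outside PEERS in any case.

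**3. How often would a PEERS cohort hold both arms?** The plan gives no figure for this. Its arm sizes are 16 completers per arm (48 in total) from 56 recruited. The 56 reproduces closely: 48 × 1.15 = 55.2, rounded up to 56; 48 / 0.85 = 56.5, rounded up to 57. Recruited per arm: 56 / 3 = 18.7, that is 18 or 19.

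Assumption, not in the documents: cohorts are filled from B and C without regard to arm.

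Large-pool formula, 1:1 allocation: P(mixed) = 1 − 2 × 0.5^k for a cohort of k.
- k = 3: 1 − 2 × 0.125 = 0.75
- k = 4: 1 − 2 × 0.0625 = 0.875
- k = 6: 1 − 2 × 0.015625 = 0.969

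Finite-arm formula: P(mixed) = 1 − [C(nB,k) + C(nC,k)] / C(nB + nC, k).

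| Cohort size k | Large pool | 16 + 16 | 18 + 19 |
|---|---|---|---|
| 3 | 0.750 | 0.774 | 0.770 |
| 4 | 0.875 | 0.899 | 0.895 |
| 6 | 0.969 | 0.982 | 0.980 |

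For example, with 16 + 16 and k = 3: 1 − (560 + 560) / 4960 = 0.774.

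**4. Do the numbers show that cohorts are mixed?** No. 16 / 3 = 5.3, so each arm could fill up to 5 single-arm cohorts of at least 3.

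**5. Which analyses are exposed?** The SAP's primary outcomes are feasibility measures in the CICADAS-Users population, with no between-arm test. The exposed analysis is the exploratory B–C comparison on family-reported scales.

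**The case against.** The strongest reply is that mixed cohorts are inferred from silence. Item 3 can be read as contrasting open forums with arm-specific sessions; on that reading its exemption only lets staff discuss an arm's own programme with that arm. This stands: the documents do not settle cohort composition. It does not close the gap, because item 2 still leaves participants free to compare apps in open groups or through private contact.

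A second reply is that a participant who sees a different app learns that the apps differ, not which one is the control. The Protocol presents the games as credible training, so this has some force, and the consent wording and group-procedures form are not available to check what families are told. Still, a social-cognition exercise beside a brick-breaking game invites a guess, in a trial about social functioning.

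A third reply is that little depends on B–C. The SAP concedes that 48 evaluated participants give too little power for an augmentation effect, several secondary measures are performance-based (for example DARE, TASSK, SCAN-3), and assessors are blinded. This stands and limits the weight of the point.

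A reader might also infer that PEERS is the one place where the two arms meet, or that the Protocol encourages contact between members. Neither is supported: open groups and private contact are also possible, and the Protocol only declines to discourage contact.

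**Conclusion.** The point holds in limited form. Participant blinding between Arms B and C is intended, and the listed safeguards do not cover the most direct way of losing it. If cohorts are filled without regard to arm, roughly three quarters of cohorts of 3 and nearly all cohorts of 6 would contain both apps.

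It is tempting to conclude that most participants will be unblinded, or that B–C will be biased towards CICADAS. The documents support neither: the percentages are the chance of sharing a cohort, no disclosure rate is given, and the direction of any bias is not established. What is at risk is the credibility of the B–C comparison on parent- and self-report secondary outcomes, and its use in planning Phase II. The primary feasibility results are not in question. This is an inexpensive improvement worth making, not a flaw that undermines the trial.

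**What to change.** 1. **Blinding, item 2.** Extend the reminder so that participants and parents are also asked not to describe or show their app to other participants. Add the same line to the group-procedures form that families already sign (Study Procedures, First Intervention Period; Confidentiality).
2. **Blinding, item 3.** Reword it so that staff do not discuss app or arm details in any setting that may include participants from more than one arm, naming PEERS sessions and cohort chats expressly. Take app questions in the individual check-ins already provided for. Deleting the exemption phrase alone is not enough: the remaining ban would still apply only to open groups or forums, and an assigned PEERS session is not one. The same edit can replace the reference to either arm, since there are three.

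It would help to state whether PEERS cohorts are single-arm or mixed, but both changes work either way.

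**Cost.** Protocol wording and one line on an existing form; no change to treatment, visits or sample size. The downside is that the app cannot be discussed in PEERS sessions, so app coaching there moves to one-to-one contact.

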### Research Monitor

This is a minimal risk protocol. There is no significant risk to using either of the web-based programs in this study, beyond the minor discomfort and tedium risks noted above. Previous studies in healthy aging, schizophrenia, and spatial neglect have not noted any significant adverse events arising from program use. Nonetheless, to follow best practices for treatment trials in medical indications, we will employ a central Research Monitor to review all unanticipated problems involving risk to participants, serious adverse effects, and any participant deaths associated with the protocol, and provide an unbiased written report of the event within ten calendar days. The research monitor will comment on the outcomes of the adverse event and relationship of the event to the protocol or test article. The research monitor will also indicate whether they concur with the details of the report provided by the PI. Reports for events determined by either the PI or Research Monitor to be possibly or definitely related to participation, and reports of events resulting in death will be promptly forwarded to the IRB.

### Withdrawal from the Protocol

Study participants may withdraw from the study at any time, for any reason, or for no stated reason. We anticipate that a common reason for study withdrawal will be the time required to complete the intervention. For participants seeking to withdraw for that reason, we will offer the alternative of discontinuing the intervention and scheduling and completing the post-intervention assessment (*End of Study, V4*) visit, given they have met the minimum sessions required to complete the assessment visits. The data analysis plan is structured so that their data will be valuable even if they do not complete the intended number of sessions. Participants who still wish to withdraw following that option will withdraw. Other than time required to use the program, we do not anticipate any common reasons for withdrawal that we will plan for in advance.

In rare cases, a Principle Investigator may decide to prematurely discontinue a participant's involvement in the study for any of the following reasons:

- a) Safety,
- b) Participant non-compliance,
- c) A change in circumstance that would prevent completion of protocol-required assessments,
- d) Participant relocation to an area that, due to great distance, would prohibit a participant from receiving follow-up at the study site,
- e) Participant displays inappropriate behavior toward study staff members or other participants,
- f) Participant is hospitalized for psychiatric reasons;
- g) Loss of funding, or;
- h) A clinical determination, by the Principal Investigator, that continuation in the study is not in the participant's best interests.

Across all reasons for withdrawal, we will ensure an orderly end to the participant's involvement in the study by arranging for the site study coordinator or PEERS clinician to recover the digital device (if it has been issued to the participant), conducting an informational interview with the participant to understand the reasons for study withdrawal and identify any issues with study conduct or adverse events that are relevant, and arrange study compensation for sessions that the participant completed.

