### Description of Protocol Devices (Software Program)

This study employs three digital-device delivered interventions: CICADAS app, Active Control app, and PEERS. Participants assigned to receive CICADAS only will be engaged in NB-SCT exercises for a total of 40 hours during the 16-week period. Participants who are assigned to receive PEERS only will be engaged in weekly 1-hour PEERS group sessions led by a PEERS clinician during the 16-week period. Participants who are assigned PEERS + CICADAS will be engaged with the exercises for a total of 40 hours and weekly 1-hour PEERS group sessions during the 16-week period. Participants who are assigned PEERS + Active Control will be engaged with the Active Control app for a total of 40 hours and weekly 1-hour PEERS group sessions during the 16-week period.

Several elements of flexibility are allowed in the schedule to accommodate the challenges that adolescents with ASD may face:

- *Location of Use:* Some participants may experience barriers to receiving treatment, including geographic location, long waiting lists, and the requirement to take time off from school for clinic visits. This intervention is available either remote and/or in-person. Every effort will be made to schedule the weekly group sessions at a time that is most convenient for the participants. The assessments and exercises are digitally-accessible, allowing participants to complete them at different locations, as convenient.
- *Variable Number of Total Sessions:* Given fatigue (common in this population), commitments to non-study activities, health issues and/or reintegration into school, work and home life, we expect that some participants will not be able to complete the weekly PEERS sessions for 16 weeks. To accommodate this, we will be understanding of their circumstances, recommend that participants complete as many sessions as their schedule permits, and explain that the results of the trial may benefit from frequent and consistent involvement in group sessions. The site study coordinator may offer their support to work with the participant on a training schedule that is feasible, given participant's current life circumstances, as appropriate. To ensure a time-bounded study commitment, after 16 weeks such participants will perform their mid-intervention assessment (V3) or post-intervention assessment (*End of Study*, V4) visits, given that they have met the minimum number of sessions required to complete this visit.

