- *Extra Time:* Under special circumstances, PEERS session(s) may be paused for 1 or more weeks. This may occur if the PEERS Clinician is unable to conduct the session and no alternate PEERS Clinician is available to conduct the session. In such cases, the intervention will be extended by the number of weeks it has been placed on hold. Participants will resume the PEERS sessions such that all 16 sessions intended for the intervention are delivered to participants.
- *Cessation of Program Use While Continuing Participation in the Study:* In some cases, a participant may wish to stop or minimize use of the program, while remaining in the study. Potential reasons for this decision might include changes in school or work circumstances, changes in residence, health issues, family/personal issues, or a lack of interest in program activities. While the participant will be encouraged to meet their weekly goals, in such cases, after discussion with the site study coordinator, the participant will be permitted to cease using the program and undergo the mid-intervention assessment (V3) or post-intervention assessment (*End of Study*, V4) visit, given they have met the minimum number of sessions required to complete this assessment.
- *Emergency:* All participants will be told how to contact the appropriate site study personnel in the case of an emergency.

Several of these options in aggregate are likely to lead to variation within a group and between groups with regard to the total number of sessions completed, and may cause an imbalance between the number of sessions completed within and between groups. Although this is not ideal, we believe that this is the correct approach given that such flexibility will allow more participants to join the study (compared to no program use flexibility), and reduce attrition. In addition, this approach has the value of more closely mimicking real-world use of the program, increasing the prospective validity of the study. We will continuously monitor the distribution of completed sessions and will consider modifications to the protocol (see *Modifications to the Protocol*) if it appears that this flexibility may be associated with meaningful differences. The data analysis plan is generally robust to variations in the number of sessions completed (see *Data Analysis*).

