### Evaluation Time Points

Week 0 –primary and secondary outcome measures are collected on all participants at baseline

Week 16 – primary and secondary outcome measures are collected on all participants

Week 32 – primary and secondary outcome measures are collected on all participants

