### Primary Outcome - Feasibility

Efforts will be made to assess all participants who have completed the minimum required intervention activities: For Arm A (CICADAS only), completing at least 1 hour of NB-SCT; for Arm B (PEERS + CICADAS), completing at least one PEERS group session and 1 hour of NB-SCT; and for Arm C (PEERS + Active Control), completing at least one PEERS group session and 1 hour of games.

As the main goal of this Phase I trial is to evaluate the feasibility, acceptability and usability of the CICADAS app, we will conduct an analysis of the following primary outcome measures in all ITT-CU participants:

1. Digital assessments completion rate. We expect that  $\geq 80\%$  of participants will complete the digital assessment battery at least twice during the CICADAS intervention;
2. NB-SCT program adherence, that is automatically tracked on the back-end data portal (percentage of training sessions completed). Based on our previous studies (CLIMB, MOODIFY, WASABI) and pilot, we expect that  $\geq 70\%$  of participants will complete 20 hours of NB-SCT;
4. Reported side effects (raw score). Based on our previous findings, we expect 0 adverse events due to program use;

5. Overall program completion rate. Based on previous findings from CLIMB and from the pilot in ASD, we hypothesize full program completion in  $\geq 70\%$  study participants.

Secondary Outcome - Preliminary Efficacy

The secondary outcome measures will be collected by trained personnel blind to treatment assignment at baseline, half-way through the intervention, and immediately after the treatment for all randomized participants. Weekly measures will capture the number of initiated or reciprocated social gatherings related to or in addition to PEERS assigned social activities.

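### Outcome assessment depends on a session minimum that differs by arm, and the withdrawal rule offers only V4, with no rule for its timing or for the week it represents

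*Protocol*

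**What the plan says.** **Who is assessed after reduced or stopped use.** Three protocol rules set a condition. Under Description of Protocol Devices, participants with fewer sessions attend V3 or V4 after 16 weeks "given that they have met the minimum number of sessions required to complete this visit". Those who stop the program but stay in the study may "undergo the mid-intervention assessment (V3) or post-intervention assessment (*End of Study*, V4) visit, given they have met the minimum number of sessions required". Under Withdrawal from the Protocol, those who want to leave because of the time required are offered "discontinuing the intervention and scheduling and completing the post-intervention assessment (*End of Study, V4*) visit, given they have met the minimum sessions required". The protocol does not say what the minimum is.

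**The minimum.** SAP, Primary Outcome - Feasibility: "Efforts will be made to assess all participants who have completed the minimum required intervention activities". It then sets the minimum by arm. Arm A has a single condition, an hour of app training. Arm B has two: "for Arm B (PEERS + CICADAS), completing at least one PEERS group session and 1 hour of NB-SCT". Arm C is treated as Arm B, with games in place of NB-SCT.

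**The opposite statement.** SAP, Evaluation Time Points: "Week 16 – primary and secondary outcome measures are collected on all participants", with the same statement for week 32. The SAP paragraph on secondary outcomes also refers to everyone randomised.

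**What V3 and V4 are.** Study Procedures places V3 after the first 16-week period and V4 after the second. Under Treatment Arms, Arms B and C have no intervention in the second period, so V3 is their end-of-treatment visit. In Arm A, V4 follows the PEERS period.

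**The concern.** There are two separate faults.

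First, site staff cannot both collect outcomes on everyone and limit assessment to those who met a minimum. If they follow the minimum, whether an outcome exists depends on behaviour after randomisation, and the test has one condition in Arm A and two in Arms B and C. The SAP's mixed model handles missing data by maximum likelihood. That is valid when missingness is explained by data in the model, but the model as described has group, time and selected baseline covariates, with no adherence term and no sensitivity analysis.

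Second, the withdrawal rule names only V4, whatever period the participant is in. For an Arm B or C participant who leaves in the first period, that bypasses the visit needed for the B1-B2 and C1-C2 comparisons. If the V4 is held on leaving, nothing in either document prevents it from being analysed as week 32. It would then stand for a no-contact period that had not taken place, which bears on the durability question (B2-B3).

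These secondary data are meant to inform the power calculation for the Phase II trial, and a missed visit cannot be recovered at analysis.

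**Working it through.** **1. The plan's own figure.** Inputs from Sample Size Justification: 48 completers, 15% non-completion, 56 recruited.
- 48 / (1 − 0.15) = 56.5, which rounds up to 57; 48 × 1.15 = 55.2, which rounds up to 56.
- Check: 56 × 0.85 = 47.6 completers; (56 − 48) / 56 = 14.3%.

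The stated 56 is reproduced to within one participant.

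**2. How high the minimum is.**
- App time: 1 / 40 hours = 2.5%.
- PEERS: 1 / 16 sessions = 6.25%.
- The SAP's own adherence benchmark: 20 / 40 hours = 50%.

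Someone with 2 hours of app time and one PEERS session is far below the benchmark and is still assessed.

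**3. The rules side by side.**

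| Place | Who is assessed | Visit |
|---|---|---|
| Protocol, Variable Number of Total Sessions | Those who met the minimum | V3 or V4, after 16 weeks |
| Protocol, Cessation of Program Use | Those who met the minimum | V3 or V4 |
| Protocol, Withdrawal from the Protocol | Those who met the minimum | V4 only |
| SAP, Primary Outcome - Feasibility | Those who met the minimum, by arm | Not named |
| SAP, Evaluation Time Points | All participants | Weeks 16 and 32 |
| SAP, secondary outcomes | All randomised | Mid-way and after treatment |

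The first four rows conflict with the last two. The second and third rows treat nearly the same person differently.

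**4. What the unequal minimum could do.** The documents give no non-start rates, so these are assumed. Let a share p never reach 1 hour of app time and a share p never attend PEERS.
- Arm A loses p. Arms B and C lose between p (same people) and 1 − (1 − p)² (independent).
- p = 5%: 5% in A; 5% to 9.75% in B and C.
- p = 10%: 10% in A; 10% to 19% in B and C.
- With 56 / 3 = 18.7 per arm, the largest excess in B or C is 18.7 × 0.0475 = 0.9 participants, or 18.7 × 0.09 = 1.7.

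B and C carry the same number of conditions, so the asymmetry touches comparisons with A, not B versus C. The SAP's ITT population already requires one PEERS session. Of the 9.75%, 5% are therefore outside it anyway, and the rule removes only 0.95 × 5% = 4.75% from it.

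**5. The withdrawal route.** Take an Arm B participant who leaves in week 6 for lack of time. The withdrawal rule offers V4 only.
- If V4 is held at week 32, its timing is right but there is no end-of-treatment value.
- If V4 is held on leaving, the measurement is from about week 6, while the SAP lists only weeks 0, 16 and 32.

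Neither document gives visit windows, an early-termination visit, or a rule assigning an off-schedule visit to a week.

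**6. How many.**
- Per arm at 15%: 18.7 × 0.15 = 2.8; from the planned counts, 8 / 3 = 2.7.
- At 30% (the pilot lost more than this): 18.7 × 0.30 = 5.6.
- If 25% to 100% of leavers go in the first period (assumed): 2 to 8 people in total at 15%, about 4 to 17 at 30%.

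These are upper bounds: some leavers will decline any visit, and others will stay in the study and have a V3 route.

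**The case against.** The case for leaving this alone has real force.

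- **Low adherers are not lost.** A reader might infer that the rule discards the low adherers a feasibility trial most needs to see. Step 2 shows otherwise: it excludes near-non-starters only. App adherence is tracked automatically, and an interview is planned for every withdrawal. This stands.
- **Misfiling is not documented.** A reader might infer that early V4 visits will be stored as week 32. No text says so, and Study Procedures would allow V4 to be held at its proper time. This stands; what can be shown is that the rule is missing.
- **V3 is not closed to everyone who stops early.** Those who stop the program but remain in the study can have V3. This also stands, and it limits the second fault to people seeking to withdraw for lack of time. The protocol expects that to be a common reason.
- **The outcomes are secondary.** The sample size is not driven by hypothesis testing, and the SAP concedes that it lacks power for an augmentation effect. This lowers the stakes.
- **The analysis is said to cope.** The protocol describes its analysis plan as robust to variation in sessions. A mixed model does use whatever data are collected, but it cannot use a visit that was never sought, and it does not supply a missing timing rule.

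What remains is the contradiction over who is assessed, the unequal condition, the missing V3 route and the missing mapping rule.

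**Conclusion.** The concern holds in limited form. The documents contradict themselves on who is assessed, and the conditional version ties missing secondary outcomes to post-randomisation behaviour, with one condition in Arm A and two in B and C. Because the minimum is so low, the loss caused by the rule itself is confined to near-non-starters. Its size by arm rests on assumed rates and on how far app and PEERS non-starters overlap; with full overlap and equal rates, the arm difference is zero.

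The withdrawal rule is a separate gap. It gives stage 1 leavers no V3, and an early V4 could be analysed as week 32 because nothing says otherwise. At the projected 15% non-completion, at most about 2.7 to 2.8 participants per arm are affected. That bound assumes every non-completer leaves in the first period and has no V3.

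The documents do not support the stronger claims that low adherers in general go unmeasured or that visits will be misfiled. No effect on the automatically tracked adherence outcome is shown.

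**What to change.** 1. Delete the session-minimum condition for assessment in both flexibility rules (Variable Number of Total Sessions; Cessation of Program Use), in Withdrawal from the Protocol, and in SAP Primary Outcome - Feasibility.
2. State that V3 at week 16 and V4 at week 32 are sought for every randomised participant who has not withdrawn consent, whatever sessions were completed.
3. In Withdrawal from the Protocol, offer those who leave in the first period V3 as well as V4.
4. Record any exit visit under its actual week, not as V4, and say in the SAP how it enters the analysis.
5. Align the SAP's ITT definition. It requires one PEERS session, and Arm A receives PEERS only in the second period, so an Arm A participant who leaves earlier is outside the primary population even if assessed. Without this change, items 1 to 3 would collect data that the primary population excludes. The other SAP populations are built on the ITT population and should be checked at the same time.

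**Cost.** Wording in both documents and a few extra visits, at about 2 hours (the protocol's figure for the same battery at V1 and V4) and $20 each. If all 8 projected non-completers attended both visits, that would be 8 × 2 = 16 visits, 16 × $20 = $320 and about 32 assessment hours. Some will decline, so the real figure will be lower.
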